#### 11.8 Health Economics

Not applicable.

## 11.9 Interim Analyses

Not applicable.

# 11.10 Sample Size Justification

Sample size calculation for the primary effectiveness hypothesis on fit success is based upon results With an assumed common standard deviation of 0.6 and expected difference of 0.25, a sample size of 80 (160 eyes) in each group will provide 83% power for a noninferiority margin of 0.5, at one-sided  $\alpha$ =0.05, based upon a two group t-test.

Document: TDOC-0053461 Version: 1.0; CURRENT; Most-Recent; Effective

Status: Effective Page 47 of 54

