#### **Sample Size Justification**

When the sample size in each group is 80 (160 eyes), a two-group t-test will have 83% power to demonstrate noninferiority with a margin of 0.5 (one-sided  $\alpha$ =0.05), assuming that the expected difference in means is 0.25 and the common standard deviation is

Document: TDOC-0053461 Version: 1.0; CURRENT; Most-Recent; Effective

Status: Effective Page 9 of 54

Sponsor: Alcon Research, Ltd.

[name]

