#### 9 TREATMENTS ADMINISTERED

Upon signing the informed consent form, subjects will be considered enrolled in the study and will be assigned a number in the appropriate numerical sequence. Subject numbers will be assigned by the electronic data capture (EDC) system at each investigational site.

Randomization for this study will be implemented in 2 parts. First, each site will be randomized to one fitting guide and will fit all subjects at their site using the assigned fitting guide (current or alternative). The purpose of this strategy is to reduce the likelihood that errors will be made in fitting the trial lenses if trying to use two similar fitting guides. Randomization of the fitting guide will be stratified by region.

Secondly, subjects who currently wear monthly/weekly contact lenses will be randomized to either AOA MF or DACP MF contact lenses (1:1 randomization). Subjects who currently wear daily disposable contact lenses will be fitted with DT1 MF contact lenses.

The study lenses will be dispensed in an unmasked manner by a trained study staff member. Subjects are unmasked to the study lenses that are dispensed, but will be masked to the fitting guides used to fit each eye for all study lenses.

Throughout the study, the Investigator will be responsible for the accounting of all study materials and will ensure that the study products are not used in any unauthorized manner.

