#### 11.4.1.2 Analysis Methods

A mixed effect repeated measures model will be utilized to test these hypotheses, including terms for fitting guide,

Correlation between eyes will be accounted for in this analysis.

Fitting guide difference (Alternative minus Current) and the corresponding one-sided 95% upper confidence limit (UCL) will be computed. Noninferiority in fitting will be declared if UCL < 0.5 at Visit 1.

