# 11.6 Multiplicity

A sequential gatekeeping strategy will be implemented to control testing of multiple effectiveness endpoints. Therefore, the overall type I error will be controlled at one-sided 0.05 with the following testing order:

Noninferiority of primary endpoint

.

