5.3.3 Device Deficiencies

The applicable definition of a device deficiency is in the study protocol. A frequency table showing counts for each Device Deficiency category will be presented. In addition, listings for treatment-emergent and pre-treatment (prior to exposure to study lenses not used for lens parametrization and fitting at Visit 1) device deficiencies will be provided.

6 Analysis Strategy for Other Endpoints

Not applicable.

7 Sample Size and Power Calculations

Sample size calculation for the primary effectiveness hypothesis on fit success is based on results [REDACTED] With an assumed common standard deviation of 0.6 and expected difference of 0.25, a sample size of 80 (160 eyes) in each group will provide 83% power for a noninferiority margin of 0.5, at one-sided $\alpha=0.05$, based on a two group t-test.

[figure not shown]
8 References

9 Revision History

This is the first revision (Version 2.0) Statistical Analysis Plan for this study. This version of the Statistical Analysis Plan is based on Version 1.0 of the study protocol.

Summary of changes:

[figure not shown]
- To update the definition of safety analysis set in order to include subjects who are lost to follow-up and their exposure to dispensed study lenses is unknown

Itemized Changes:

Section	Information Changed
Section 2.1	The following was added: Subjects who are lost to follow-up and their exposure to dispensed study lenses is unknown will be included in the safety data set. The dispense date for these subjects will be assumed as the first exposure date (Visit 2 Dispense 1).

[figure not shown]
10 Appendix

Table 10-1 Overview of Study Plan

	Visit 1	Visit 2 Dispense 1 / Visit 2 Dispense 2	Visit 3 Follow Up 1 / Visit 3 Exit	USV
Procedure/ Assessment	Screening and Fitting	Dispensing 0-7 days from Visit 1	Day 10 ± 3 – Follow-up / Exit	Unscheduled Visit
Randomization • Site to Fitting Guide	✓ *			
Informed Consent	✓			
Demographics	✓			
Medical History	✓			
Concomitant Medications/ Changes in Concomitant Medications	✓	✓	✓	✓
Subjective (Manifest) refraction	✓	(✓)	(✓)	(✓)
BCVA † (with manifest refraction)	✓	(✓)	(✓)	(✓)

Study contact lens parameters optimization and fitting †	✓			
Inclusion/Exclusion	✓			
Randomization	✓ **			
Weekly/Monthly Subject to study lens				
Dispense study lenses		✓ **		
Biomicroscopy	✓	✓	✓	✓
Assess optimal prescription			✓ ^e	(✓)
Assess AEs	✓ ^f	✓	✓	✓
Assess device deficiencies	✓	✓	✓	✓
Exit Form	(✓)	(✓)	✓	(✓)

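### The stated 83% power assumes 80 independently randomised subjects per guide, but the guide is randomised to about 20 sites, so the figure does not describe this design

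*Protocol*

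**What the plan says.** Protocol section 11.10 gives the inputs, "With an assumed common standard deviation of 0.6 and expected difference of 0.25", and the method, "based upon a two group t-test", and concludes that "a sample size of 80 (160 eyes) in each group will provide 83% power for a noninferiority margin of 0.5". The Synopsis agrees ("a two-group t-test will have 83% power to demonstrate noninferiority with a margin of 0.5"), as does SAP section 7 ("a sample size of 80 (160 eyes) in each group will provide 83% power"). The Synopsis gives 160 subjects as required and 180 as planned.

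On allocation, Protocol section 9 says that "each site will be randomized to one fitting guide and will fit all subjects at their site using the assigned fitting guide", with this randomisation stratified by region; SAP section 1.2 repeats it. Protocol section 8 gives about 20 sites with about 9 subjects each. Only the choice between two of the lens brands is randomised subject by subject, and that is not the primary comparison.

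The decision rule in Protocol section 11.4.1.2 is "Noninferiority in fitting will be declared if UCL < 0.5 at Visit 1", using a one-sided 95% limit. Section 11.6 says that "the overall type I error will be controlled at one-sided 0.05". The model code in SAP section 4.3.1 has fixed effects for guide, lens, their interaction, region and ADD power, and a covariance structure for the two eyes of a subject. It has no site term.

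**The concern.** The primary contrast compares one set of sites with another. Subjects at a site share the fitters, and the endpoint, the number of trial lenses tried on each eye, partly counts what the fitter does. Some variation between sites is therefore plausible, although the documents say nothing of its size. Any such variation inflates the variance of the guide difference, and the number of randomised units, rather than of subjects, limits the degrees of freedom. None of the three sizing statements mentions sites per guide, an ICC or a design effect.

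The 83% and the requirement of 160 subjects are the stated basis for judging whether the study can reach a conclusion. If noninferiority is missed under a valid analysis, a reader who relies on 83% may count the miss against the alternative guide when the design had less power than stated.

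**Working it through.** **Inputs from the documents.** Margin 0.5, expected difference 0.25, SD 0.6, one-sided alpha 0.05, 80 subjects per guide (160 required) or 90 (180 planned), about 20 sites.

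**Assumptions, because the documents are silent.** Ten sites per guide, so m = 8 or 9 subjects per site. ICC of 0 to 0.20, defined on subject means. A valid site-level test with 20 − 2 = 18 degrees of freedom. No reduction in variance from adjusting for region, lens or ADD power.

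**Step 1: reproduce the stated figure.** The distance to the margin is 0.5 − 0.25 = 0.25. The standard error is 0.6 × √(2/80) = 0.0949. The noncentrality is 0.25 / 0.0949 = 2.635. With 158 degrees of freedom, the noncentral t gives 83.6%. Treating the 160 eyes per group as independent would give 98%. So the plan's figure counts subjects, not eyes, and contains no allowance for site.

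**Step 2: allow for site.** Divide the noncentrality by √DE, where DE = 1 + (m − 1) × ICC, and use 18 degrees of freedom. Example for 160 subjects at ICC 0.05: DE = 1 + 7 × 0.05 = 1.35; noncentrality = 2.635 / √1.35 = 2.268; power 70%.

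**Step 3: both readings of the SD.** If 0.6 is the SD between subjects, use it directly. If it is per eye, the SD of a subject's two-eye mean is 0.6 × √((1 + ρ)/2). With an assumed between-eye correlation ρ = 0.5, that is 0.6 × √0.75 = 0.520.

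| SD reading | Subjects | ICC 0 | ICC 0.05 | ICC 0.10 | ICC 0.20 |
|---|---|---|---|---|---|
| Subject | 160 | 81% | 70% | 62% | 50% |
| Subject | 180 | 85% | 74% | 64% | 51% |
| Per eye, ρ = 0.5 | 160 | 90% | 81% | 73% | 60% |
| Per eye, ρ = 0.5 | 180 | 93% | 84% | 75% | 61% |

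Over ICC 0.05 to 0.20, power runs from 84% down to 50%, so the chance of a miss runs from 16% to 50%. The plan implies 100% − 83% = 17%.

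**Step 4: largest ICC that keeps 83%.** With the subject-level SD there is none at 160 subjects (81% even at ICC 0); at 180 it is about 0.009, a between-site SD of about 0.6 × √0.009 = 0.06 lenses. With the per-eye SD it is about 0.04 at 160 and 0.05 at 180. If the ICC is defined on the variance of a single eye instead, these last two limits become about 0.03 and 0.04, so the scale has to be stated.

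**Step 5: the SAP model as coded** (normal approximation, subject-level SD). Without a site term the model uses the unclustered standard error (SE) while the estimate varies by SE × √DE. At ICC 0.05:
- 160 subjects: SE 0.0949 and true standard error 0.1102. The chance of declaring noninferiority is Φ((0.25 − 1.645 × 0.0949) / 0.1102) = Φ(0.852) = 80%. The one-sided error is 1 − Φ(1.645 / √1.35) = 7.8%.
- 180 subjects: DE = 1 + 8 × 0.05 = 1.40, SE 0.0894 and true standard error 0.1058. The chance is Φ(0.972) = 83%, with a one-sided error of 8.2%.

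**The case against.** **The size is assumed.** This stands. No ICC is given, and the unit of the 0.6 SD is not stated. A reader might infer that the plan understates the chance of a miss in every case, for example that it is at least 25%. The documents do not support that. Miss rates of 26% to 50% over ICC 0.05 to 0.20 need the subject-level SD. On the per-eye reading at ICC 0.05, the miss rate is about 19% at 160 subjects and 16% at 180, and the latter is no worse than stated.

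**The SAP does not plan a site-level test.** This also stands, and a reader should not infer that the trial as coded would fail at the rates in the table. At ICC 0.05 (subject-level SD) the coded model still declares noninferiority 80% to 83% of the time. It does so only because the one-sided error rises to about 8%, so this is not 83% power at the promised 0.05.

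**There are mitigating features.** Visit 1 supplies the primary endpoint, and the full analysis set includes subjects exposed only to trial-fit lenses. Later dropout therefore removes little, and the 180 rows are nearer the expected case. Stratifying by region and adjusting for region, lens and ADD power may lower both the relevant ICC and the residual SD. The documents do not say by how much.

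**The arithmetic is right.** For the method named, it is. A reader might infer a calculation error, but there is none: the method does not match the allocation.

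**Text is redacted.** Part of the sizing sentence and of the model description is blacked out. The stated figure nevertheless reproduces with no clustering allowance, and the SAP code is visible without site.

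**Conclusion.** The concern holds as a mismatch between design and power statement. The 83% belongs to a trial that randomises 80 independent subjects per guide; this one randomises about 20 sites. That much rests on the documents alone and is firm.

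The size of the loss is not firm. It depends on an ICC the documents do not give, the unit of the SD, an equal split of sites, and a valid site-level analysis. Under those assumptions, power at the planned 180 subjects for ICC 0.05 to 0.20 is 74% down to 51% with a subject-level SD, and 84% down to 61% with a per-eye SD. The stated figure is safe only if sites barely differ on the first reading, or differ modestly on the second. The documents do not show which case applies, so they support restating the figure but not a claim that the trial is badly underpowered.

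**What to change.** In the Synopsis, Protocol section 11.10 and SAP section 7, replace the two-group t-test power with power for a site-randomised comparison. State:
- the number of sites per guide and subjects per site;
- the design effect, 1 + (m − 1) × ICC;
- the site-level degrees of freedom: 18 for 20 sites, or fewer after adjusting for region (16 if the three places in the Synopsis, US, Canada and EU, are the strata, which is an inference; this lowers power by less than half a percentage point);
- whether the 0.6 SD is per eye or per subject and, if per eye, the assumed between-eye correlation;
- the scale on which the ICC is defined;
- power over a stated ICC range, such as 0 to 0.20, for both 160 and 180 subjects.

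No subjects need be added, and enrolment and conduct stay as they are. The cost is wording in three places and a less favourable stated figure.

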#### 12 ADVERSE EVENTS AND DEVICE DEFICIENCIES

#### 12.1 General Information

An AE is any untoward medical occurrence, unintended disease or injury, or untoward clinical signs (including abnormal laboratory findings) in subjects, users, or other persons, whether or not related to the investigational medical device (test article). Refer to the Glossary of Terms for categories of AEs and SAEs.

Figure 12–1 Categorization of All Adverse Events

[figure not shown]
[figure not shown]

Figure 12-2 Categorization of All Serious Adverse Events

Document: TDOC-0053461 Version: 1.0; CURRENT; Most-Recent; Effective

Status: Effective Page 48 of 54

#### **12.2 Monitoring for Adverse Events**

At each visit, after the subject has had the opportunity to spontaneously mention any problems, the Investigator should inquire about AEs by asking the standard questions:

- "Have you had any health problems since your last study visit?"
- "Have there been any changes in the medicines you take since your last study visit?"

Changes in *any protocol-specific parameters and/or questionnaires* evaluated during the study are to be reviewed by the Investigator. Any untoward (unfavorable and unintended) change in *a protocol-specific parameter or questionnaire response* that is clinically relevant, in the opinion of the Investigator, is to be reported as an AE. These clinically relevant changes will be reported regardless of causality.

## 12.3 Procedures for Recording and Reporting

AEs are collected from the time of informed consent. Any pre-existing medical conditions or signs/symptoms present in a subject prior to the start of the study (ie, before informed consent is signed) are not considered AEs in the study and should be recorded in the Medical History section of the eCRF.

In addition, temporary lens awareness or visual changes during the fitting process are not considered AEs if the Investigator assesses that the symptom(s) can reasonably resolve within the anticipated adaptation period.

For each recorded event, the ADEs and SAEs documentation must include: date of occurrence, severity, treatment (if applicable), outcome, and assessments of the seriousness and causality. In addition, the Investigator must document all device deficiencies reported or observed with test and control articles on the Device Deficiency eCRF. The site must submit all available information on ADEs, SAEs, and device deficiencies to the Study Sponsor immediately as follows:

- All SAEs must be reported immediately (within 24 hours) of the Investigator's or site's awareness.
- ADEs that do not meet seriousness criteria and device deficiencies must be reported within 10 calendar days of the Investigator's or site's awareness.
- A printed copy of the completed Serious Adverse Event and Adverse Device Effect and/or Device Deficiency eCRF must be included with product returns. [Refer to CLK027-P001 MOP for instructions on product returns.]

Document: TDOC-0053461 Version: 1.0; CURRENT; Most-Recent; Effective

Status: Effective Page 49 of 54

 Additional relevant information after initial reporting must be entered into the eCRF as soon as the data become available.

- Document any changes to concomitant medications on the appropriate eCRFs.
- Document all relevant information from Discharge Summary, Autopsy Report,
   Certificate of Death, etc, if applicable, in narrative section of the Adverse Device
   Effect (for related AEs) and Serious Adverse Event eCRF.

Note: Should the EDC system become non-operational, the site must complete the appropriate paper Serious Adverse Event and Adverse Device Effect and/or Device Deficiency Form. The completed form is faxed or emailed to the Study Sponsor at according to the timelines outlined above; however, the reported information must be entered into the EDC system once it becomes operational.

Any AEs and device deficiencies for non-study marketed products (ie, habitual contact lens care products) used concomitantly during the study will be considered and processed as spontaneous (following the postmarket vigilance procedures) and should be communicated to the product's manufacturer as per local requirements.

Study Sponsor representatives may be contacted for any protocol-related question and their contact information is provided in the Manual of Procedures that accompanies this protocol.

Further, depending upon the nature of the AE or device deficiency being reported, the Study Sponsor may request copies of applicable portions of the subject's medical records. The Investigator must also report all AEs and device deficiencies that could have led to a SADE according to the requirements of regulatory authorities or IEC/IRB.

#### **Intensity and Causality Assessments**

Where appropriate, the Investigator must assess the intensity (severity) of the AE based upon medical judgment with consideration of any subjective symptom(s), as defined below:

#### Intensity (Severity)

Mild An AE is mild if the subject is aware of but can easily tolerate the sign or symptom.

Moderate An AE is moderate if the sign or symptom results in discomfort significant enough to cause interference with the subject's usual activities.

Print Date: Print Date:

Document: TDOC-0053461 Version: 1.0; CURRENT; Most-Recent; Effective

Status: Effective Page 50 of 54

Severe An AE is severe if the sign or symptom is incapacitating and results in the

subject's inability to work or engage in their usual activities.

For every AE in the study, the Investigator must assess the causality (Related or Not Related to the medical device or study procedure). An assessment of causality will also be performed by Study Sponsor utilizing the same definitions, as shown below:

#### Causality

Related An AE classified as related may be either definitely related or possibly related

where a direct cause and effect relationship with the medical device or study procedure has not been demonstrated, but there is a reasonable possibility that

the AE was caused by the medical device or study procedure.

Not Related An AE classified as not related may either be definitely unrelated or simply

unlikely to be related (ie, there are other more likely causes for the AE).

The Study Sponsor will assess the AEs and may upgrade the Investigator's assessment of seriousness and/or causality. The Study Sponsor will notify the Investigator of any AEs that is upgraded from non-serious to serious or from unrelated to related.

## 12.4 Return Product Analysis

Study Sponsor representatives and their contact information are provided in the MOP that accompanies this protocol.

Alcon products associated with device deficiencies and/or product related AEs should be returned and must include the Complaint # which will be provided by Study Sponsor after the case is entered in the Study Sponsor's Global Product Complaint Management System. To maintain study team masking, device deficiency and ADE returns may be collected by the end of the study along with all other supplies returns.

# 12.5 Unmasking of the Study Treatment

Masked information on the identity of the assigned fitting guide should not be disclosed to the subject during the study [See Section 9.4 for additional detail on study masking]. If the treatment code needs to be broken in the interest of subject safety, the Investigator is encouraged to contact an appropriate Study Sponsor representative prior to unmasking the information if there is sufficient time. Dependent upon the individual circumstances (ie, medical emergency), the code may be broken prior to contact with the Study Sponsor. The

Document: TDOC-0053461 Version: 1.0; CURRENT; Most-Recent; Effective

Status: Effective Page 51 of 54

Study Sponsor must be informed of all cases in which the code was broken and of the circumstances involved. Additionally, the Study Sponsor may be required to unmask the information in order to fulfill expedited regulatory reporting requirements.

## 12.6 Follow-Up of Subjects with Adverse Events

The PI is responsible for adequate and safe medical care of subjects during the study and for ensuring that appropriate medical care and relevant follow-up procedures are maintained after the study.

The PI should provide the Study Sponsor with any new safety information (which includes new AEs and changes to previously reported AEs) that may affect the safety evaluation of the device. For AEs that are unresolved/ongoing at time of subject exit from study, any additional information received at follow-up should be documented in the eCRFs up to study completion (ie, database lock).

Any additional data received up to 1 month after subject discontinuation or exit must be documented and available upon the Study Sponsor's request. All complaints received after this time period will be considered and processed as spontaneous (following the postmarket vigilance procedures) and should be communicated to Alcon as the medical device's manufacturer per local requirements.

# 12.7 Pregnancy in the Clinical Trial

Pregnancy should be included in the Medical History section of the eCRF when a pregnant woman enters the study or if a woman becomes pregnant during the study. Pregnancy is not reportable as an AE; however, complications may be reportable and will be decided on a case—by-case basis.

Document: TDOC-0053461 Version: 1.0; CURRENT; Most-Recent; Effective

Status: Effective Page 52 of 54

# 13 DATA HANDLING AND ADMINISTRATIVE REQUIREMENTS

## 13.1 Completion of Source Documents and Case Report Forms

The nature and location of all source documents will be identified to ensure that original data required to complete the eCRFs exist and are accessible for verification by the site monitor. If electronic records are maintained, the method of verification must be determined in advance of starting the study. At a minimum, source documents should include the following information for each subject:

- Subject identification (name, sex, race/ethnicity)
- Documentation of subject eligibility
- Date of informed consent
- Dates of visits
- Documentation that protocol specific procedures were performed
- Results of study parameters, as required by the protocol
- Trial medication accountability records
- Documentation of AEs and other safety parameters (if applicable)
- Records regarding medical histories and the use of concomitant therapies prior to and during the study
- Date of trial completion and reason for early discontinuation, if applicable

It is required that the author of an entry in the source documents be identifiable. Direct access to source documentation (medical records) must be allowed for the purpose of verifying that the data recorded on the eCRF are consistent with the original source data.

Electronic CRFs will be provided to the sites; only designated individuals may complete the eCRFs. The eCRFs will be submitted at regular intervals based upon the clinical trial visit schedule. It is expected that all data reported will have corresponding entries in the source documents and that the PI will review the reported data and certify that the eCRFs are accurate and complete. No subject identifiers should be recorded on the eCRFs beyond subject number, and demographic information.

Document: TDOC-0053461 Version: 1.0; CURRENT; Most-Recent; Effective

Status: Effective Page 53 of 54

